5.1.1 Retesting During Screening or Lead-in Period

Retesting of laboratory parameters and/or other assessments within any single Screening or Lead-in period will be permitted (in addition to any parameters that require a confirmatory value).

Any new result will override the previous result (ie, the most current result prior to first dose) and is the value by which study inclusion will be assessed, as it represents the patient's most current clinical state.

5.2 Study Materials

The site will provide all required materials for the tests performed locally (ie, relevant to clinical laboratory tests). The site will have available a well-calibrated scale for recording body weight, a calibrated sphygmomanometer, and thermometer for temperature. The site will have a validated temperature-controlled refrigerator. The site will provide all materials required for accurate source documentation of study activities.

BMS will provide a BMS-approved protocol and any amendments or administrative letters (if required). Case report forms (electronic or hard copy) will be provided by BMS. Nivolumab will be supplied by BMS. BMS will also provide the Investigator Brochure and the EORTC QLQ-C30 and EQ-5D-3L.

5.3 Safety Assessments

Only data for the procedures and assessments specified in this protocol should be submitted to BMS on a case report form. Additional procedures and assessments may be performed as part of standard of care; however, data for these assessments should remain in the patient's medical record and should not be provided to BMS unless specifically requested. NCI CTCAE version 4.0 will be the criteria used to assess severity of AEs.

During the 100 days after the last dose of study treatment, patients will have 2 additional follow-up visits as described in [Table 5.1-3](#).

The following assessments should be monitored starting on Cycle 1 Day 1 and will continue as per the schedule in the Time and Events Tables at the specified frequency until discontinuation from study therapy:

- Adverse events continuously throughout the study
- Physical examination and physical measurements including weight and ECOG PS
- Complete blood count with differential, including white blood cells, lymphocyte count, absolute neutrophil count, hemoglobin, hematocrit, and platelet count. Results to be obtained prior to dosing on infusion days.
- Serum chemistry tests (blood urea nitrogen or serum urea level, serum creatinine, sodium, calcium, phosphate, chloride, glucose, lipase, and LDH). Results to be obtained prior to dosing on infusion days. Amylase should be performed in addition to lipase in cases where lipase results are not available prior to dosing.
- Liver function tests including AST, ALT, total bilirubin, alkaline phosphatase, and albumin. Results to be obtained prior to dosing on infusion days.

- Thyroid function testing including thyroid stimulating hormone (free T3 and free T4 if abnormal results for TSH)

5.3.1 Imaging Assessment for the Study

Any incidental findings of potential clinical relevance that are not directly associated with the objectives of the protocol should be evaluated and handled by the Study Investigator as per standard medical/clinical judgment.

5.3.2 Vital Signs and Physical Examinations

Vital signs (seated blood pressure and heart rate), physical measurements, and physical examinations should be performed at program visits.

A full physical examination should be performed prior to the start of treatment. A targeted physical examination may be performed by a qualified professional guided by the examiner's observations and/or patient complaints on new or changed conditions, symptoms, or concerns. Targeted physical exam includes assessment of heart, lungs, and abdomen.

5.3.3 Pregnancy Testing

Pregnancy testing must be completed for WOCBP every 4 weeks while receiving the program drugs and during the follow-up period of 100 days, which includes Follow-up Visits 1 and 2. Pregnancy testing may be performed at home if an in-office visit is otherwise not required. Telephone contacts are required to obtain results for all patients who perform post-treatment at-home pregnancy testing. Although testing may be performed with home pregnancy testing kits, any positive result must be confirmed by serum pregnancy testing at the program site.

5.4 Efficacy Assessments

Efficacy assessments include initial mandatory tumor assessment at Week 12 (\pm 5 days). Further tumor assessments to be completed as required by local standards of care or at the investigator's discretion and are recommended every 8 weeks, as discussed in [Table 5.1-2](#).

Study evaluations will take place in accordance with [Table 5.1-2](#) and should be performed according to RECIST 1.1 criteria.

High resolution CT with oral or IV contrast or contrast-enhanced MRI are the preferred imaging modalities for assessing radiographic tumor response. If a patient has a known allergy to contrast material, please use local prophylaxis standards to obtain the assessment with contrast if at all possible or use an alternate modality. In cases where contrast is strictly contraindicated, a non-contrast scan will suffice. Screening assessments should be performed within 6 weeks prior to first dose of study drug. Brain MRI is the preferred imaging method for evaluating CNS metastasis, and an assessment is required during screening. If known or new CNS metastases are detected during screening, a brain scan is required at the mandatory tumor assessment at Week 12 (\pm 5 days). Furthermore, all known or suspected sites of disease should be assessed at screening and at subsequent assessments using the same imaging method and technique. If more than one method is used at screening, then the most accurate method according to RECIST 1.1 should be used when recording data and should again be used for all subsequent assessments. Bone scan, PET scan, or

ultrasound is not adequate for assessment of RECIST response. In selected circumstances where such modalities are the sole modality used to assess certain non-target organs, those non-target organs may be evaluated less frequently. For example, bone scans may need to be repeated only when complete response is identified in the target disease or when progression in bone is suspected. Previously treated CNS metastases are not considered measurable lesions for purposes of RECIST determined response.

Tumor measurements should be made by the same investigator or radiologist for each assessment whenever possible. Changes in tumor measurements and tumor responses to guide ongoing study treatment decisions should be assessed by the investigator using RECIST 1.1 at Week 12 and using investigator-assessed response thereafter.

Per Amendment 08, patients or their caregivers will be contacted following progression every 3 months either by direct contact or via telephone until death, withdrawal of consent, or lost to follow up for up to 2 years from the start of their treatment with nivolumab. Overall survival will be followed continuously while patients are on the study drug and at follow up visits 1 and 2 as well as every 3 months after discontinuation, or progression, for up to 2 years following the start of therapy either by direct contact (office visits) or via telephone contact, until death, withdrawal of study consent, or lost to follow-up. Overall survival is defined as the time between the start of treatment and the date of death due to any cause. See [Table 5.1-3](#) for further clarification.

Per Amendment 08, survival will be followed after progression either by direct contact (office visits) or via telephone contact until death, withdrawal of study consent, or lost to follow-up for 2 years following start of therapy.

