Changes in tumor measurements and tumor responses to guide ongoing study treatment decisions should be assessed by the investigator using RECIST 1.1.

Per Amendment 08, the EQ-5D-3L and survival follow up will be collected for up to 2 years from the first dose of study therapy or until death, withdrawal of study consent, or lost-to-follow-up as indicated in the assessment table.

Statistical Considerations:

Sample Size: With an approximate 15% screening failure rate, a cohort of 735 screened PS1 patients is projected to a yield 640 treated patients. With $n = 640$ patients, about 3 will experience a rare adverse event with 0.5% true cumulative event rate with a rate estimated within 95% confidence interval (CI) (0.2%-1.1%). Approximately 2 patients with events and a 95% CI of (0%-1.1%) for assumed true event rate of 0.3% are projected.

Endpoints: The primary endpoint is the incidence for high-grade (CTCAE v4.0 Grade 3 or higher), treatment-related, select adverse events.

The secondary endpoints include:

- Incidence of all high-grade (Grades 3 and higher), select adverse events
- Median time to onset and median time to resolution (Grades 3-4) of select adverse events
- OS
- Investigator-assessed ORR

[REDACTED]

[REDACTED]

[REDACTED]

[REDACTED]

[REDACTED]

Analyses: The evidence for the research hypothesis of this clinical trial that high-grade (CTCAE v4.0 Grade 3 or higher), treatment-related select adverse events occur with a low frequency in patients with advanced (unresectable or metastatic) melanoma will be presented in terms of the number, percentage of subjects, and 95% confidence interval for the percentage with these select adverse events during treatment and off-treatment overall and by cohort.

Adverse events from date of enrollment up to last contact with patients will be presented for the full study duration and separately for events that occur on- or post-treatment. In particular, safety data will be summarized and listed for all treated patients using the NCI CTCAE version 4.0. All on-study AEs, drug-related AEs, SAEs, and drug-related SAEs will be tabulated using worst grade per NCI CTCAE v4.0 criteria by system organ class and MedDRA preferred term. On-study laboratory parameters including hematology, chemistry, liver function, thyroid function, and renal function will be summarized using worst grade per NCI CTCAE v4.0 criteria.

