Laboratory Tests	X		X (TFTs only)	CBCs with differential, ^a Serum chemistry tests, ^b liver function tests ^c and lipase should be checked every cycle, and the results should be obtained prior to dosing. TFTs ^d should be checked every 3 cycles (every 6 weeks) starting with Cycle 1. May be completed more frequently if required by local standards. Laboratory tests should be completed 72 hours prior to dosing, and the results must be available prior to dosing. See footnote b regarding availability of lipase results prior to dosing.
Pregnancy Test		X		Completed every 2 cycles, starting with Cycle 1. May be completed more frequently if required by local standards

Table 5.1-2: CA209172 On-Treatment Assessments

Procedure	Each Cycle (every 2 weeks) (±2 days)	Every 2 Cycles (every 4 weeks) (±2 days)	Every 3 Cycles (every 6 weeks) (±2 days)	Notes
Efficacy Assessments				
Tumor Scans	---	---see notes---		Mandatory initial tumor assessment is to be completed at Week 12 (±5 days). If known or new CNS metastases are detected during screening, a brain scan is required at the mandatory tumor assessment at Week 12 (±5 days). Further tumor assessments are recommended to be completed as required by local standards of care or at the investigator's discretion and are recommended every 8 weeks. The assessment of clinical benefit should be balanced by clinical judgment as to whether the patient is clinical deteriorating and unlikely to receive any benefit from continued treatment with nivolumab.
Survival	X			
Outcomes Assessments				
EQ-5D-3L		X		Every 2 cycles (4 weeks) for 4 months starting with Cycle 1, then every 4 cycles (8 weeks) after first administration of nivolumab prior to any study procedures and treatments
EORTC QLQ-C30		X		Every 2 cycles (4 weeks) for 4 months starting with Cycle 1, then every 4 cycles (8 weeks) after first administration of nivolumab prior to any study procedures and treatments
Clinical Drug Supplies				
Administration of Study Drug	X			

BP = blood pressure; CBC = complete blood count; HR = heart rate; LDH = lactate dehydrogenase; LFT = liver function test; NCI CTCAE = National Cancer Institute Common Terminology Criteria for AEs; O2 = oxygen; PS = Performance Status; RR = respiratory rate; TFT, thyroid function test.

^a CBCs with differential includes white blood cell count, lymphocyte count, absolute neutrophil count, hemoglobin, hematocrit, and platelet count. Results to be obtained prior to dosing on infusion days

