- b Serum chemistry tests include blood urea nitrogen [BUN] or serum urea level, serum creatinine, sodium, calcium, chloride, lipase, and glucose. Amylase should be performed in addition to lipase in cases where lipase results are not available prior to dosing.
- c Liver function tests include AST, ALT, total bilirubin, alkaline phosphatase, albumin.
- d Thyroid function testing including TSH (free T3 and free T4 if abnormal results for TSH).

Table 5.1-3: Off-Treatment Follow-Up Assessments:CA209172

Procedure	Every 4 Weeks	FU-X01 (30 days ±7 days)	FU-X02 (70-84 days after FU- X01 ±7 days)	Follow-Up After X01 and X02. Every 3 months. (±7 days)	Notes
Safety Assessments					
Physical Examinations		X	X		Collect weight and ECOG PS. Focused physical examination may be performed if clinically indicated.
Vital Signs and Oxygen Saturation		X	X		Temperature, BP, HR, RR, O2 saturation by pulse oximetry at rest (also monitor amount of supplemental oxygen if applicable) prior to dosing and at any time a patient has any new or worsening respiratory symptoms.
Adverse Events Assessments		X	X		Beyond 100 days from the last dose of study therapy, patients followed for ongoing drug-related adverse events until resolved, symptoms return to baseline or are deemed irreversible, lost to follow-up, or withdrawal of study consent.
		■	■		
Laboratory Tests		X	X		Serum chemistry tests and TFTs should be checked at FU1 and FU2.
Pregnancy Test	X	X	X		Pregnancy testing may be performed at home if an in-office visit is otherwise not required.
Efficacy Assessments					
Tumor Scans				-----see notes-----	Tumor progression scans are recommended to be completed as required by local standards of care or at the investigator's discretion.

Table 5.1-3: Off-Treatment Follow-Up Assessments:CA209172

Procedure	Every 4 Weeks	FU-X01 (30 days ±7 days)	FU-X02 (70-84 days after FU- X01 ±7 days)	Follow-Up After X01 and X02. Every 3 months. (±7 days)	Notes
Survival Follow-up		X	X	X ^a	
Outcomes Assessments					
EQ-5D-3L		X	X	X ^a	The EQ-5D-3L can be completed by mail, e-mail, or telephone call (using the telephone version) when a clinical visit is not otherwise required. When a clinical visit is required, the questionnaire should be completed at the clinic.

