8.3.2 Secondary Endpoint(s)

The secondary endpoints include:

- Incidence of all high-grade (Grades 3 and higher), select adverse events
- Median time to onset and median time to resolution (Grades 3-4) of select adverse events
- OS is defined as the time from first dosing date to the date of death. A patient who has not died will be censored at last known date alive. OS will be followed continuously while patients are on treatment and every 3 months via in-person or phone contact after patients discontinue the study drug.

- Investigator-assessed ORR. ORR is defined as the number and percentage of patients with a best overall response (BOR) of confirmed CR or PR. ORR as assessed by the investigator will be reported.

[REDACTED]

[REDACTED]

[REDACTED]

[REDACTED]

[REDACTED]

[REDACTED]

[REDACTED]

[REDACTED]

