2 STUDY DESCRIPTION

2.1 Study Design

The study will include subjects with histologically-confirmed stage III (unresectable) or stage IV advanced melanoma who have documented progression after treatment containing an anti-CTLA-4 monoclonal antibody. Subjects will be treated with 3 mg/kg of nivolumab IV every 2 weeks for a maximum of 24 months. Subjects will undergo screening evaluations to determine eligibility within 6 weeks prior to the first dose following the signing of an informed consent. Each 14-day dosing period will constitute a cycle.

The Scientific Steering Committee will evaluate the clinical risk/benefit ratio closely following a defined Safety Management Plan.

Subjects will undergo screening evaluations to determine eligibility prior to first dose following signed informed consent. Subject's demographic data will be collected: date of birth, gender, disease stage, date of diagnosis, previous treatments, comorbidities, performance status, lactate dehydrogenase (LDH) level, type of melanoma (mucosal, uveal), and mutation status if known (BRAF, NRAS, cKIT).

Safety, including adverse events and physical examination, should be monitored continually, and safety assessments are discussed in Tables 5.1-1 and 5.1-2 of the protocol.

Mandatory initial tumor assessments are to be done at Week 12 (± 7 days). Further tumor assessments should be performed according to institutional standard of care and are recommended every 8 weeks until:

- disease progression
- a concurrent malignancy requires treatment
- the subject is lost to follow up
- the subject withdraws study consent
- completed 24 months of treatment

Subjects will not be permitted to continue their treatment beyond initial Investigator-assessed progressive disease unless they meet the following criteria:

- Investigator-assessed clinical benefit
- Subject is tolerating study drug

The investigator should use his or her clinical judgment to assess clinical benefit by considering whether the subject is clinically deteriorating and unlikely to receive any benefit from continued treatment with nivolumab.

Follow up begins when the decision to discontinue a subject from study therapy is made (no further treatment with nivolumab) and continues up to 5 years from first dose of study therapy until death, withdrawal of study consent, or lost-to-follow-up.

The cohorts are described in Table 1.

Table 1: Subject Cohorts

[figure not shown]
(Cohort Number)	Disease Criteria

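### Confirmed ORR depends on optional scans and on contradictory response criteria after Week 12, while the SAP analyses a different, unconfirmed Week 12 rate

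*Protocol*

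**What the plan says.** **Endpoint.** Protocol 8.3.2 states that "ORR is defined as the number and percentage of patients with a best overall response (BOR) of confirmed CR or PR". The synopsis and Section 8.4.3 repeat this. The visible text gives no confirmation rule or interval. Section 8.4 reports ORR on the response evaluable set, which under Section 8.2 needs a dose, a baseline scan and one post-baseline scan.

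**Schedule.** Section 5.4: "Efficacy assessments include initial mandatory tumor assessment at Week 12". After that: "Further tumor assessments to be completed as required by local standards of care or at the investigator's discretion and are recommended every 8 weeks". Table 5.1-2 agrees ("Further tumor assessments are recommended to be completed as required by local standards of care"), and so does the off-treatment Table 5.1-3 ("Tumor progression scans are recommended to be completed as required by local standards of care").

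**Criteria.** Section 5.4 says that responses guiding treatment decisions are "assessed by the investigator using RECIST 1.1 at Week 12 and using investigator-assessed response thereafter". An earlier sentence of that section puts study evaluations under RECIST 1.1 with no time limit. The synopsis says: "Changes in tumor measurements and tumor responses to guide ongoing study treatment decisions should be assessed by the investigator using RECIST 1.1".

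**SAP.** Section 7.5.1 defines the overall response rate as CR or PR at Week 12 over the number treated, with Clopper-Pearson intervals and no mention of confirmation. SAP 3.2 and 4.2, as visible, do not list ORR. SAP 6.3 defines a response evaluable set, but 7.5.1 does not use it. SAP 2.1 also has a different window: "Mandatory initial tumor assessments are to be done at Week 12 (± 7 days"), against ±5 days in the protocol.

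**The concern.** A confirmed response needs two consistent assessments, and the protocol requires one after baseline. A patient with a PR at Week 12 and no later scan has met the scan requirement of the response evaluable set. That patient stays in the denominator but cannot enter the numerator. The loss runs in one direction, its size follows local imaging practice and not the drug, and a larger sample does not reduce it.

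The criteria add a second problem. A site that follows the last part of the 5.4 sentence may judge the confirming scan, or a response first seen after Week 12, on a basis other than RECIST 1.1. A site that follows the rest of 5.4 or the synopsis would not. Pooled responses could then rest on mixed criteria.

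Third, the two documents would report different quantities under nearly the same name. A reader could not tell whether a published figure is confirmed best response among evaluable patients or single-time-point response among all treated.

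**Working it through.** The documents give no sample size, precision or power figure for ORR, so there is none to reproduce. The check is a count, a comparison and an illustration.

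**1. Count of required assessments**
- Mandatory post-baseline assessments: 1 (Week 12).
- Minimum for a confirmed response: 2 (the finding and its confirmation).
- Required assessments left to confirm a Week 12 response: 1 − 1 = 0.
- Next recommended scan: 12 + 8 = Week 20, optional.

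This holds however the RECIST wording is read.

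**2. The two definitions side by side**

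| | Protocol 8.2, 8.3.2, 8.4 | SAP 7.5.1 |
|---|---|---|
| Response | best overall, confirmed | CR or PR, confirmation not mentioned |
| Time point | any | Week 12 |
| Denominator | response evaluable | all treated |
| Status | secondary endpoint | not listed in visible SAP 3.2 or 4.2 |

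The differences pull in opposite directions. Dropping confirmation raises the rate. Counting Week 12 only, and keeping treated patients without a post-baseline scan in the denominator, lowers it. The documents do not allow the net difference to be signed.

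**3. Illustration of the loss from missing confirmation**

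Inputs:
- Response rate p: 20% (6 of 30, sequenced cohorts of CA209-004) and 32% (CA209037), both from Protocol 1.4.1.1. Their use for this trial is an assumption.
- Share of responders lacking a confirming assessment, m: 10% to 20%. This is an assumption, because the documents give no rescan rate.
- n = 800, the maximum treated (Protocol Section 8).

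Formulas: loss = p × m; half-width = 1.96 × √(p(1 − p)/n).

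| p | loss, m = 10% | loss, m = 20% | half-width, n = 800 |
|---|---|---|---|
| 20% | 0.20 × 0.10 = 2.0 points | 0.20 × 0.20 = 4.0 points | 1.96 × √(0.16/800) = 2.8 points |
| 32% | 0.32 × 0.10 = 3.2 points | 0.32 × 0.20 = 6.4 points | 1.96 × √(0.2176/800) = 3.2 points |

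For p = 32%, with Clopper-Pearson 95% intervals at n = 800:
- all confirmed: 32.0% (28.8 to 35.4)
- 90% confirmed: 28.8% (25.6 to 32.0)
- 75% confirmed: 24.0% (21.1 to 27.1)

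The response evaluable set cannot exceed the number treated, so the true half-width is at least this wide. At n = 640 and p = 32% it is 1.96 × √(0.2176/640) = 3.6 points.

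**The case against.** The best counter-argument is SAP 7.5.1. The protocol sends readers to the SAP for analysis details, and the SAP's Week 12 rate can be computed from the one mandatory scan. A missing second scan cannot lower it. That is correct, and it means that the loss above applies to the protocol's endpoint and not to the SAP's statistic. It does not remove the problem, because the protocol's endpoint is then left without a visible analysis. Redacted SAP text might hold more, so this is a statement about the visible plan only.

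Standard-of-care scanning after Week 12 is stated consistently and looks deliberate. That stands, and it is why the remedy should not add a mandatory scan.

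Several stronger readings are tempting but unsupported:
- *Section 5.4 drops RECIST 1.1 after Week 12.* The sentence concerns responses that guide treatment decisions, and the same section elsewhere applies RECIST 1.1 without a time limit. This is an internal contradiction.
- *No response can be confirmed.* Optional later scans can confirm one, and the Week 12 scan could confirm a response seen on an earlier unscheduled scan. What is missing is a required confirming assessment.
- *The bias exceeds sampling error.* With 10% lacking confirmation it is at or below the half-width. A confirming scan read on other criteria could also move ORR either way.
- *The 32% is the trial's comparator.* It is background and came from central review, whereas this endpoint is investigator-assessed.
- *Patients who stop drug before Week 12 have no scheduled assessment.* Table 5.1-3 has no mandatory scan, but Section 3.1 states the Week 12 assessment without limiting it to patients on drug. The point is unclear, not settled.

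**Conclusion.** The concern holds for the protocol's confirmed ORR. No required assessment can confirm a Week 12 response, Section 5.4 conflicts with itself and with the synopsis on criteria after Week 12, and unconfirmed responders count as non-responders. Confirmed ORR can therefore be biased downward. Under the assumed rates the loss is about 2 to 6 points, against a half-width of about 3 points: from somewhat below sampling error to about twice it. The 10% to 20% share lacking confirmation has no source in the documents, so the size is illustrative. The direction for responders never rescanned follows from the definitions alone.

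The mismatch between protocol and SAP on confirmation, time point and denominator is a matter of text and needs no assumption. ORR is estimated, not tested, and is secondary. The different Week 12 windows are a minor item.

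**What to change.** 1. Adopt one ORR definition in both documents, covering confirmation (with its rule, if kept), time point and denominator, and give ORR the same status in each.
2. State that RECIST 1.1 applies to every tumor response recorded for the endpoint. Reconcile the 5.4 sentence on assessment after Week 12 with the rest of that section and the synopsis. This concerns the endpoint record; how treatment decisions are guided is for the sponsor to settle.
3. In the SAP, report confirmed and unconfirmed responses separately, give the number of responders with no later RECIST assessment, and show the Week 12 rate from the mandatory scan alongside.
4. Use one Week 12 window in both documents.

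The cost is wording plus a few extra tables, and a less simple headline ORR. No additional mandatory scan is needed. Protocol 8.4 has the SAP finalized before database lock, so item 3 can be done up to that point even if scanning is complete.
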